8.1 Overall trial design

The present trial is a phase I, double-blind, parallel, randomised, and placebo-controlled trial of the chlamydia vaccine, CTH522, in healthy adults. The trial will be conducted at Imperial College Healthcare NHS Trust (ICHT), London, in the UK.

[figure not shown]
It is planned to randomly assign 66 subjects into six cohorts. Cohorts A-D investigate CTH522-CAF01 administered IM in two doses (85 µg and 15 µg). Cohort E investigates CTH522-CAF09b administered IM in one dose (85 µg). Cohort F is the placebo group (Figure 1). The enrolled subjects will complete 12 trial visits (Vs) (Table 3).

All subjects in the active groups (cohort A-E) will receive three IM injections of the adjuvanted CTH522 and some (cohort B and C) will receive the non-adjuvanted CTH522 via the TO or ID route (given at the same time as the 2nd and 3rd IM vaccinations). All active groups will receive TO administration as a boost at Day 140 of either the non-adjuvanted CTH522 (12 µg in each eye) or placebo.

- Cohort A will receive three IM vaccination of 85 µg CTH522-CAF01. This cohort is divided into two groups: A1 will receive ID placebo at Day 28 + Day 112, and TO placebo at Day 140, while A2 will receive TO placebo at Day 28 + Day 112, and non-adjuvanted TO CTH522 boost at Day 140.
- Cohort B will receive three IM vaccinations of 85 µg CTH522-CAF01. This cohort is divided into two groups: B1 will receive TO vaccination of the non-adjuvanted CTH522 at Day 28 and 112 and TO placebo at Day 140, while B2 will receive the same for Day 28 and 112, but non-adjuvanted TO CTH522 boost at Day 140. The two additional TO doses of CTH522 (12 µg in each eye) are administered in each eye. The rationale for this schedule is to investigate the impact of simultaneous TO administration of the antigen on the immunogenicity results.
- Cohort C will receive three IM vaccinations of 85 µg CTH522-CAF01. This cohort is divided into two groups: C1 will receive ID vaccination of the non-adjuvanted 24 µg CTH522 at Day 28 and 112 and TO placebo at Day 140, while C2 will receive the same for Day 28 and 112, but TO 12 µg CTH522 boost in each eye at Day 140. The rationale for this schedule is to investigate the impact of simultaneous ID administration of the antigen on the immunogenicity results.
- Cohort D will receive three IM vaccinations of 15 µg CTH522-CAF01. The rationale for the A and D cohorts is to investigate the impact of the two IM CTH522 doses on the immunogenicity results.

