At V4 (Day 28), the AEs and CM are reviewed and recorded. Vital signs are taken. Eye and symptom-directed physical examinations are performed. Refer to Table 3 for eye examination method required at V4. Before the vaccinations, blood samples for safety and immunogenicity determination (please refer to type of tests in Table 4) are drawn, and urine for pregnancy and ocular samples are taken. The subjects receive the 2nd IM vaccinations together with ID or TO vaccination as specified in the Figure 1. In the event that the first TO vaccinations are planned for several subjects on the same day, there should be a minimum of two hours between the TO dosing for each subject. The two hour lagging between the TO doses should be performed for the first five subjects receiving TO doses and can be discontinued after the first these five subjects if there are no safety concerns. The subjects are observed for any immediate AE for 60 minutes after the vaccination. The diary card is issued with instructions before discharge from the site.

At V5 (Day 42), the diary card is collected and reviewed, AEs and CM are reviewed and recorded. Vital signs and ocular samples are taken. Eye and symptom-directed physical examination are performed. Refer to Table 3 for eye examination method required at V5. Blood samples for safety and immunogenicity (please refer to type of tests in Table 4) are drawn.

At V6 (Day 56), the AEs and CM are recorded. Eye and symptom-directed physical examination are performed. Refer to Table 3 for eye examination method required at V6. Blood samples for immunogenicity determination are drawn (please refer to type of tests in Table 4). Ocular sample is taken.

At V7 (Day 112), the AEs and CM are recorded. Vital signs are taken. Eye and symptom-directed physical examinations are performed. Refer to Table 3 for eye examination method required at V7. Before the vaccinations, blood samples for safety and immunogenicity determination (please refer to type of tests in Table 4) are drawn, and urine for pregnancy and ocular samples are taken. The subjects receive the 3rd IM vaccinations together with ID or TO vaccination as specified in the Figure 1. The subjects are observed for any immediate AE for 60 minutes after the vaccination. The diary card is issued with instructions before discharge from the site.

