In the trial, it will be investigated if the TO or ID vaccination with CTH522 given concomitantly with CTH522-CAF01 IM will lead to increased immune responses. The TO dose of CTH522 is 24 µg, therefore the ID dose of CTH522 is also 24 µg, given as 100 µl ID.

The CAF01 adjuvant human dose was based on the results from the ACAF01-01 trial, a CAF01 dose-escalation trial completed in the Netherlands. The results of the ACAF01-01 trial concluded that a 625 µg/125 µg of DDA/TDB in CAF01 is the optimal human dose [12]. Also, this dose was found efficient when combined with CTH522 in the first-in-human clinical trial (CHLM-01) [9].

The CAF09b adjuvant is, like CAF01, a liposomal adjuvant formed by DDA and incorporating the MMG glycolipid into the liposome membrane for both stability and immunostimulatory reasons. The human dose level of CAF09b was therefore set based on the CAF01 dose levels of DDA and glycolid (TDB in CAF01 vs MMG in CAF09b), being 625 µg/125 µg of DDA/MMG in CAF09b. In addition to the DDA and MMG, the CAF09b contains the TLR3 agonist poly I:C, electrostatically bound to the liposome surface.

The poly I:C level had in pre-clinical studies (as the adjuvant CAF09) being at the same dose level as MMG. From a formulation and stability perspective, however, a lower dose of poly I:C relative to DDA/MMG was found optimal, resulting in 31 µg poly I:C combined with 625 µg/125 µg DDA/MMG to give CAF09b. This CAF09b 625/125/31 µg DDA/MMG/poly I:C was tested and found safe and acceptable in a repeated dose toxicological study in rabbits (as part of a toxicology study for a cancer vaccine) as well as the two ongoing clinical trials.

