**Table 2: Treatment labels**

Day and treatment	Cohort	Label
Day 0		
85 µg IM CTH522-CAF01	A1, A2, B1, B2, C1, C2	Cohort A-C CTH-01-all
15 µg IM CTH522-CAF01	D1, D2	Cohort D CTH-01-low
85 µg IM CTH522-CAF09b	E1, E2	Cohort E CTH-09
IM Placebo	F1, F2	Cohort F Placebo
Day 28 and 112		
85 µg IM CTH522-CAF01 + ID Placebo	A1	Cohort A1 CTH-01+ID-PCB
85 µg IM CTH522-CAF01 + TO Placebo	A2	Cohort A2 CTH-01+TO-PCB
85 µg IM CTH522-CAF01 + TO CTH522	B1, B2	Cohort B CTH-01+TO
85 µg IM CTH522-CAF01 + ID CTH522	C1, C2	Cohort C CTH-01+ID
15 µg IM CTH522-CAF01 + TO Placebo	D1	Cohort D1 CTH-01-low+TO-PCB
15 µg IM CTH522-CAF01 + ID Placebo	D2	Cohort D2 CTH-01-low+ID-PCB
85 µg IM CTH522-CAF09b + TO Placebo	E1	Cohort E1 CTH-09+TO-PCB
85 µg IM CTH522-CAF09b + ID Placebo	E2	Cohort E2 CTH-09+ID-PCB
IM Placebo + TO Placebo	F1	Cohort F1 Placebo+TO-PBO
IM Placebo + ID Placebo	F2	Cohort F2

Placebo+ID-PCB		
Day 140		
85 µg IM CTH522-CAF01 + ID Placebo + TO Placebo	A1	Cohort A1 CTH-01+ID-PCB+TO-PCB
85 µg IM CTH522-CAF01 + TO Placebo + TO CTH522	A2	Cohort A2 CTH-01+TO-PCB+TO
85 µg IM CTH522-CAF01 + TO CTH522 + TO Placebo	B1	Cohort B1 CTH-01+TO+TO-PCB
85 µg IM CTH522-CAF01 + TO CTH522	B2	Cohort B2 CTH-01+TO
85 µg IM CTH522-CAF01 + ID CTH522 + TO placebo	C1	Cohort C1 CTH-01+ID+TO-PCB
85 µg IM CTH522-CAF01 + ID CTH522 + TO CTH522	C2	Cohort C2 CTH-01+ID+TO
15 µg IM CTH522-CAF01 + TO Placebo	D1	Cohort D1 CTH-01-low+TO-PCB
15 µg IM CTH522-CAF01 + ID Placebo + TO CTH522	D2	Cohort D2 CTH-01-low+ID-PCB+TO
85 µg IM CTH522-CAF09b + TO Placebo	E1	Cohort E1 CTH-09+TO-PCB
85 µg IM CTH522-CAF09b + ID Placebo + TO CTH522	E2	Cohort E2 CTH-09+ID-PCB+TO
IM Placebo + TO Placebo	F1	Cohort F1 Placebo+TO-PCB
IM Placebo + ID Placebo + TO Placebo	F2	Cohort F2 Placebo+ID-PCB+TO-PCB

The full treatment will be explained in footnotes. In the above CTH-01 is an abbreviation for CTH522-CAF01, and CTH-09 for CTH522-CAF09b.

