#### 5.1 Statistical Considerations

Baseline is defined as the last assessment with available data prior to the first administration of trial medication. Day 0 is the day of first administration with IMP. Assessments from scheduled visits will be presented when available, otherwise the first unscheduled visit succeeding the scheduled visit in question is used.

Categorical data will be summarized by treatment group, using number and percentages of subjects. For calculation of percentages the denominator will either be the number of subjects in the analysis set or the number of subjects in the analysis set with non-missing values. Continuous data will be presented using the number of subjects (n), mean, standard deviation (SD), median, minimum, and maximum if nothing else is stated. Both the absolute values and the change from baseline will be presented.

Descriptive statistics for all endpoints will be presented by treatment group and visit (if applicable) using observed cases, i.e., no imputation of missing data will be performed.

All statistical tests will be two-sided and performed on a 5 % significance level. Estimated treatment differences and 95 % confidence intervals (CI) will be presented together with the corresponding p-value.

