### 7.3.1 Anti-CTH522 IgG Antibody

The anti-CTH522 IgG titre will be summarised by visit: Number of subjects with available titre, geometric mean, geometric coefficient of variation (CV), median, minimum, and maximum will be presented for actual values and ratio to baseline (fold difference).

Percentage of subjects achieving seroconversion for anti-CTH522 IgG at any time point after first vaccination will be presented for

- 4-fold increase compared to baseline
- 10-fold increase compared to baseline

The number and percentage of subjects achieving 4-fold increase respectively 10-fold increase seroconversion for anti-CTH522 IgG will be summarised by visit including cumulative numbers over

time. If a subject achieves seroconversion at a visit, the same subject will be counted as having seroconversion at all subsequent visits in the cumulative summary.

In addition to the descriptive presentation outlined above, the following analyses which are not described in the protocol will be presented:

The anti-CTH522 IgG titre will be compared by a non-parametric Mann-Whitney-Wilcoxon exact two-sample test for

- Cohort A-C vs Cohort D at Day 28
- Cohort A-C vs Cohort E at Day 28
- Cohort A vs Cohort B at Day 126
- Cohort A vs Cohort C at Day 126
- Cohort B vs Cohort C at Day 126
- Cohort A vs Cohort D at Day 126
- Cohort A vs Cohort E at Day 126

Using SAS® Proc NPAR1WAY with option *exact wilcoxon*.

If the value of anti-CTH522 IgG is below lower limit of quantification (LLOQ), then the value is set to LLOQ to be able to calculate the change.

The anti-CTH522 IgG titre will also be presented on a log scale in a spaghetti-plot by subject and day. The geometric mean will be presented in a plot by treatment group and day.

The cumulative proportion of subjects achieving 4-fold increase respectively 10-fold increase seroconversion for anti-CTH522 IgG will be presented in a plot by treatment group and day. In addition, a plot showing the median titre will be presented by treatment group and day.

All data will be listed.

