## 7.7 Multiplicity Adjustments

Several Fishers exact test will be calculated for the co-primary endpoints, and several nonparametric Wilcoxon tests will be calculated for the comparisons of anti-CTH522 IgG titre. They should all be interpreted with care when evaluating the results.

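### The three route contrasts (A vs B, A vs C, B vs C) at Day 126 leave out the Day 28 titre, a pre-route covariate that would add precision if it is at least moderately correlated with the Day 126 titre

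*SAP*

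**What the plan says.** **Test.** SAP 7.3.1 states: "The anti-CTH522 IgG titre will be compared by a non-parametric Mann-Whitney-Wilcoxon exact two-sample test for" a list of seven contrasts. Three concern route, A vs B, A vs C and B vs C, and all are at Day 126 ("Cohort A vs Cohort B at Day 126"). No covariate, stratum or change score is named. Ratio to baseline appears only in the descriptive summaries, and SAP 5.1 defines baseline as the last value before the first dose, not Day 28. SAP 5.1 adds: "All statistical tests will be two-sided and performed on a 5 % significance level". It also promises an estimated difference with a 95% CI beside each p-value, but SAP 7.3.1 names neither for these tests.

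**What A, B and C share.** SAP Table 2 puts "A1, A2, B1, B2, C1, C2" under one Day 0 regimen, 85 µg IM CTH522-CAF01, and SAP 7.3.1 pools A-C for its Day 28 tests. Protocol 8.1 says that the TO and ID doses are "given at the same time as the 2nd and 3rd IM vaccinations", so none precedes Day 28. For the Day 28 visit (V4), Protocol 8.2 says: "Before the vaccinations, blood samples for safety and immunogenicity determination (please refer to type of tests in Table 4) are drawn". Protocol Table 4 schedules the serum IgG ELISA at that visit.

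**The question served.** Protocol 9.2.1 says that "it will be investigated if the TO or ID vaccination with CTH522 given concomitantly with CTH522-CAF01 IM will lead to increased immune responses". The second secondary objective asks for the serum IgG response to TO or ID given together with the IM vaccine.

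**The concern.** Subjects differ in how strongly they respond to the IM vaccine. In A, B and C the Day 28 titre records that response before the cohorts diverge. The Day 0 titre cannot do this, because it precedes any vaccination. A bare comparison at Day 126 leaves these differences in the error term. To the extent that Day 28 predicts Day 126, a real effect of the added route is then more likely to be missed, although the trial already collects the value that would remove part of the noise. These three are the only planned significance tests of the added-route question on serum IgG, and no sample size calculation was made, so the analysis is where precision can still be gained.

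**Working it through.** The documents state no power, precision or sample-size figure, so there is nothing of the plan's own to reproduce.

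**1. Is Day 28 a legitimate covariate?** It falls after randomisation, which would normally rule it out. Up to the V4 blood draw, however, A, B and C have been treated identically, so the route cannot have affected it. Conditioning on it does not bias A vs B, A vs C or B vs C. For A vs D (dose) and A vs E (adjuvant) the first dose differs, so Day 28 is already an outcome.

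**2. Inputs.**
- Cohort size: assumed, because the numbers per group are in a figure that is not shown. Protocol 11.4.3 gives 91% active: 0.91 × 66 ≈ 60, and 60/5 = 12 if the five active cohorts are equal. Range checked: 10 to 15.
- True difference: 1 SD of log titre, assumed for illustration.
- ρ, the within-cohort correlation of log Day 28 and log Day 126 titre: not given; 0 to 0.7 shown.
- Share of Day 28 titres at LLOQ: not given; none or half shown.
- Alpha: two-sided 5% (SAP 5.1).

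**3. Variance.** With N = 24 subjects in a contrast, the variance of the adjusted difference relative to the unadjusted one, including the cost of estimating one slope, is (1 − ρ²) × (1 + 1/(N − 4)) = (1 − ρ²) × 1.05. For ρ = 0.5: 0.75 × 1.05 = 0.788, and √0.788 = 0.887. Break-even is at ρ² = 1 − 1/1.05 = 0.048, so ρ ≈ 0.22.

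**4. Power by simulation**, normal log titres, 12 vs 12, 1-SD difference:

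| ρ | Variance ratio | SE ratio | Exact Wilcoxon (planned) | Rank ANCOVA | Log-titre ANCOVA | Log-titre ANCOVA, half of Day 28 at LLOQ |
|---|---|---|---|---|---|---|
| 0 | 1.050 | 1.025 | 0.60 | 0.61 | 0.63 | – |
| 0.3 | 0.956 | 0.977 | 0.61 | 0.65 | 0.68 | 0.66 |
| 0.5 | 0.788 | 0.887 | 0.61 | 0.72 | 0.74 | 0.72 |
| 0.7 | 0.536 | 0.732 | 0.61 | 0.85 | 0.89 | 0.80 |

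The columns do not all come from one run, and repeat runs differ by one or two points. Simulated false-positive rates were 0.046–0.048 (Wilcoxon), 0.052–0.057 (ANCOVA) and 0.050–0.053 (rank ANCOVA).

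The 63% at ρ = 0 is not a gain from Day 28. It arises because a normal-theory test is slightly more powerful than the exact Wilcoxon test when log titres really are normal. Rank ANCOVA against Wilcoxon is the like-for-like comparison.

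**5. Detectable difference at 80% power** (normal approximation, covariate cost left out): (1.960 + 0.842) × √(2/12) = 1.14 SD unadjusted. Multiplying by √(1 − ρ²) gives 1.09, 0.99 and 0.82 SD at ρ = 0.3, 0.5 and 0.7.

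**6. Other cohort sizes.** Unadjusted Wilcoxon power is about 0.51 with 10 per cohort and 0.72 with 15. The SE ratios at ρ = 0.3, 0.5 and 0.7 barely move: 0.983, 0.893, 0.736 with 10, and 0.972, 0.883, 0.728 with 15.

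**The case against.** **Nothing in the plan is wrong.** A reader might infer that the unadjusted test is biased or invalid. It is neither: under randomisation the exact Wilcoxon test holds its level. This stands, and the point is one of efficiency only.

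**The tests carry little weight.** The secondary endpoint is seroconversion, presented descriptively. The Wilcoxon tests are additions to the protocol in a phase I trial, without multiplicity control, and SAP 7.7 says of the tests: "They should all be interpreted with care when evaluating the results". This also stands, and it limits the consequence.

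**Serum IgG is not the main route question.** A reader might conclude that the trial's central question about route is compromised. The protocol's Introduction gives the main purpose of adding TO and ID as the ocular immune response, and ocular antibodies are exploratory and reported separately. The point reaches only the serum IgG objective.

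**The gain is conditional.** It is tempting to say flatly that the route contrasts lose precision. The documents do not support that, because they give no correlation. Between the two samples lie 126 − 28 = 98 days and two further IM doses, so a low correlation is possible. Below about 0.2 there is nothing to gain, and flooring at LLOQ reduces the gain further. The counterweight is that the loss at zero correlation is small: a 2.5% larger standard error.

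**The form of adjustment matters.** Applying the Wilcoxon test to residuals from a regression without a cohort term would leave part of the route effect in the slope. That version loses about 1–2 points of power at correlation 0–0.2 and reaches only about 0.63 at 0.3, so ANCOVA with a cohort term is preferable.

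**Conclusion.** The point holds as a conditional loss of efficiency in three supplementary tests. For A, B and C the Day 28 titre is a valid pre-route covariate, it is already collected, and SAP 7.3.1 does not use it. At a correlation of 0.5 the standard error would fall by about 11% and power would rise from about 61% to about 74% (72% with rank ANCOVA). At 0.7 the fall is about 27% and power about 89% (85%). At 0.3 the standard error falls by only about 2%. With half of the Day 28 titres at LLOQ, log-titre ANCOVA gives about 66%, 72% and 80% at 0.3, 0.5 and 0.7. These figures assume 12 per cohort, a 1-SD difference and normal log titres; the correlation and the share at LLOQ are unknown. The improvement is cheap and worth making. It corrects no error, and it does not extend to the D or E contrasts.

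**What to change.** Before unblinding, add to SAP 7.3.1, for A vs B, A vs C and B vs C at Day 126 only:

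- an ANCOVA of log Day 126 titre on cohort and log Day 28 titre, reported as a geometric mean ratio with 95% CI and p-value, which also supplies the estimate and interval promised in SAP 5.1;
- rank ANCOVA as the non-parametric version;
- the unadjusted exact Wilcoxon test, kept alongside;
- a rule that subjects without a Day 28 titre are left out of the adjusted analysis and not imputed, in line with SAP 7.6;
- a statement that the Day 28 titre is not a covariate for the D or E contrasts, where it is already an outcome.

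List the addition in SAP section 8.

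Cost: a few lines of SAP text and code, with no new data. The downsides are one degree of freedom, a modelling assumption on the log scale (which the rank version avoids), the loss of any subject without a Day 28 titre from the adjusted analysis, and negligible benefit if the correlation is below about 0.2.

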## 7.4 Exploratory immunogenicity endpoints

[figure not shown]
The exploratory immunogenicity endpoints are

- Systemic and ocular antibodies
  - Cell-mediated immune response measured by Elispot and/or flow cytometry
  - Antibody responses measured by T- and B-cell Elispot
  - Serum neutralising antibodies against serovars D-G
- Isolation and characterisation of CTH522–antigen-specific memory B-cells in the systemic compartments (dependent on the elicited specific memory T- and B-cell numbers)

and will be handled in a separate report.

## 7.5 Interim Analysis

No interim analysis is planned.

## 7.6 Handling of Missing Values

No imputation of missing data is planned.

## 7.7 Multiplicity Adjustments

Several Fishers exact test will be calculated for the co-primary endpoints, and several nonparametric Wilcoxon tests will be calculated for the comparisons of anti-CTH522 IgG titre. They should all be interpreted with care when evaluating the results.

## 7.8 Sub-group and Centre Effects

No sub-group analyses are planned.

Adjustments for centre effects are not applicable in this single centre trial.

## 8 Deviations from Protocol

- The periods where the events for three of the co-primary endpoints (solicited local injection site reactions, solicited ocular reactions, and solicited systemic reactions) are considered were not specified in the protocol but in the subjects' diary. In this SAP the vaccination days are detailed as well as the 14-day period after vaccinations.
- For the co-primary endpoint *Solicited systemic reactions after IM and/or ID administration*, the PT *Pyrexia* should be used for temperatures above 38.3°C only, which is not as in the FDA guidelines presented in the protocol Appendix 1. Appendix 1 is stating temperatures above 38.0°C. For increased temperatures at or below 38.3°C, the PT *Body temperature increased* is used and thus not included as events. If the temperature is unknown, *Pyrexia* will be used, and the event included.
- The Wilcoxon tests of anti-CTH522 IgG titre are not described in the protocol.
- Presentations and analyses are adapted to fit the nature of the data.

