8.7 Safety assessments

The trial staff must record all AEs, non-serious and serious, expected and unexpected in the relevant form of the eCRF. This starts from the time after the subject has signed the informed consent form (ICF) at V1 until the end-of-trial at V12.

The source of AEs covers, for example, the subject's response to questions about his/her health (a standard non-leading question), information from diary card, symptoms spontaneously reported by a subject, results from pre-defined laboratory testing and examinations where the findings are assessed by the investigator to be clinically significant changes or abnormalities, and other information relating to the subject's health becoming known to the investigator (for example hospitalisation).

The subjects will remain at the site for 60 minutes after each vaccination so that any immediate AEs observed may be recorded. It is also documented if no immediate AEs occurred. Trial staff will ensure that the subjects have a diary card, ruler to measure and thermometer to enable them to record AEs while away from the clinical site.

From the day of vaccination until seven days later, solicited AEs and unsolicited AEs will be recorded through the use of diary cards. Between Day 7–14, the subject will be asked to fill in details in the diary *only* if they experience an AE or if any medications were taken.

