#### 7.1.1 Solicited injection site reactions

Solicited injection site reactions after IM and/or ID administration are defined as AEs with the following PTs:

- Injection site erythema
- Injection site pruritus
- Injection site pain (covers both the lower level terms *injection site tenderness* and *injection site pain*)
- Injection site swelling
- Injection site warmth

occurring in the period after and up to and including 14 days after Day 0, Day 28, and Day 112 vaccination.

The number and percentage of subjects and the number of events will be presented by PT:

- At Day 0 for the four treatment regimens present

- Cohort A-C
- Cohort D
- Cohort E
- Cohort F
- At Day 28 and Day 112 for the 10 treatment regimens present
  - Cohort A1
  - Cohort A2
  - Cohort B
  - Cohort C
  - Cohort D1
  - Cohort D2
  - Cohort E1
  - Cohort E2
  - Cohort F1
  - Cohort F2

The number and percentage of subjects with events occurring in the period after and up to and including 14 days after the Day 0 vaccination and the corresponding 95% CI will be presented together with a pairwise comparison of number of subjects with events using Fishers exact test for the following:

- Cohort A-C vs Cohort D
- Cohort A-C vs Cohort E
- Cohort A-C vs Cohort F

All information will be listed.

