### 7.1.2 Solicited ocular reactions

[figure not shown]
Solicited local reactions after TO administration are defined as AEs with the following PTs:

- Lacrimation increased
- Swelling of eyelid
- Ocular hyperaemia
- Ocular discomfort

occurring in the period after and up to and including 14 days after Day 28, Day 112, and Day 140 vaccinations.

The number and percentage of subjects and the number of events will be presented by PT:

- At Day 28 and Day 112 for the five TO treatment regimens
  - Cohort A2
  - Cohort B
  - Cohort D1

- Cohort E1
- Cohort F1
- At Day 140 for the 11 TO treatment regimens present, where the placebo cohort (F) will be regarded as one
  - Cohort A1
  - Cohort A2
  - Cohort B1
  - Cohort B2
  - Cohort C1
  - Cohort C2
  - Cohort D1
  - Cohort D2
  - Cohort E1
  - Cohort E2
  - Cohort F

The number and percentage of subjects with events occurring in the period after and up to and including 14 days after the Day 28 and the Day 112 vaccinations and the corresponding 95% CI will be presented by visit together with a pairwise comparison of number of subjects with events using Fishers exact test for the following:

- Cohort B vs Cohort A2
- Cohort B vs Cohort F1

All information will be listed.

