### 7.1.3 Solicited systemic reactions

[figure not shown]
Solicited systemic reactions after IM and/or ID administration are defined as AEs with the following PTs:

- Pyrexia
- Chills
- Myalgia
- Rash

occurring in the period after and up to and including 14 days after the Day 0, Day 28, and Day 112.

*Pyrexia* should be used as PT for temperatures above 38.3°C only, which is not as in the FDA guidelines presented in the protocol Appendix 1 stating temperatures above 38.0°C. For increased temperatures at or below 38.3°C, the PT *Body temperature increased* is used and thus not included as events. If the temperature is unknown, *Pyrexia* will be used, and the event included.

The number and percentage of subjects and the number of events will be presented by PT:

- At Day 0 for the four treatment regimens present
  - Cohort A-C
  - Cohort D
  - Cohort E
  - Cohort F
- At Day 28 and Day 112 for the 10 treatment regimens present
  - Cohort A1
  - Cohort A2
  - Cohort B
  - Cohort C
  - Cohort D1
  - Cohort D2
  - Cohort E1
  - Cohort E2
  - Cohort F1
  - Cohort F2

The number and percentage of subjects with events occurring in the period after and up to and including 14 days after the Day 0 vaccination and the corresponding 95% CI will be presented together with a pairwise comparison of number of subjects with events using Fishers exact test for the following:

- Cohort A-C vs Cohort D
- Cohort A-C vs Cohort E
- Cohort A-C vs Cohort F

All information will be listed.

[figure not shown]

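### Three co-primary solicited endpoints count events to Day 14, but protocol 8.7 solicits them for seven days only; SAP section 8 overlooks this and the SAP never separates the two periods

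*SAP*

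**What the plan says.** **Collection (protocol 8.7).** "From the day of vaccination until seven days later, solicited AEs and unsolicited AEs will be recorded through the use of diary cards". Between Day 7 and Day 14 the diary stays with the subject, but it is completed only "if they experience an AE or if any medications were taken". The same section has all adverse events recorded in the eCRF from consent at V1 to the end of the trial at V12.

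**Diary return (protocol 8.2 and Table 3).** The diary is collected at V3, V5, V8 and V11. Each visit is allowed 12 to 16 days after the preceding vaccination.

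**Endpoint definitions (protocol 7.4, 10.1.1, 11.4.4).** The reactions are listed without a time window.

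**Counting windows (SAP).**
- Injection-site reactions, SAP 7.1.1: "occurring in the period after and up to and including 14 days after Day 0, Day 28, and Day 112 vaccination".
- Ocular reactions, SAP 7.1.2: "occurring in the period after and up to and including 14 days after Day 28, Day 112, and Day 140 vaccinations".
- Systemic reactions, SAP 7.1.3: "occurring in the period after and up to and including 14 days after the Day 0, Day 28, and Day 112".

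**What makes a reaction solicited (SAP 7.1.1).** "Solicited injection site reactions after IM and/or ID administration are defined as AEs with the following PTs". SAP 7.1.2 and 7.1.3 use the same construction. The test is the preferred term and the date, not how the event was collected.

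**The SAP's explanation (SAP section 8).** The periods in which events for these endpoints "are considered were not specified in the protocol"; the section names the subjects' diary as their source instead. Protocol 8.7 is not mentioned.

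**The concern.** In the first week the subject is asked about each listed reaction. In the second week an entry appears only if the subject decides that something is worth recording. A myalgia, rash or red eye first noted on Day 12 enters the co-primary rate exactly as one noted on Day 2 does, although it was collected less intensively and is more likely to be unrelated to the vaccine. The reported percentage is then neither a seven-day solicited rate nor a uniformly solicited 14-day rate.

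These are the trial's primary endpoints. They carry 95% confidence intervals and the Fisher tests in SAP 7.1.1 to 7.1.3. Background events in week 2 raise the rate in every cohort and pull the cohorts closer together, even when the background is the same in all of them. The SAP plans no Day 0-7 versus Day 8-14 split and no seven-day sensitivity analysis, so the summary tables would not show how much of a rate comes from week 2.

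**Working it through.** The plan states no figure to reproduce: there is no sample size calculation and no assumed reaction rate. The check compares the texts, counts days, and adds an illustration on assumed rates.

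**1. The texts compared**

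| Item | Protocol | SAP |
|---|---|---|
| Listed reactions actively recorded | vaccination to Day 7 (8.7) | not addressed |
| Day 7-14 | diary entry only if an AE occurs or medication is taken (8.7) | counted as solicited (7.1.1-7.1.3) |
| Window attached to the endpoint | none (7.4, 10.1.1, 11.4.4) | up to and including 14 days |
| Stated source of the window | none | subjects' diary (section 8) |

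**2. Day count**
- Post-vaccination days counted: 14. Beyond the solicited period: Days 8-14, so 14 - 7 = 7 days, and 7/14 = 50%.
- Earliest permitted diary collection: Day 12. A subject seen then has no diary for Days 13 and 14, although AEs can still be recorded at visits.
- With a Day 0-7 window, no counted day lies beyond the solicited period.

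**3. Effect on a background rate (assumed rates)**

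Let w be the seven-day background risk and c the capture in week 2 relative to week 1. Then P(14 days) = 1 - (1 - w)(1 - c·w).

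| w | c = 1 | c = 0.5 |
|---|---|---|
| 2% | 4.0% | 3.0% |
| 5% | 9.8% | 7.4% |
| 10% | 19.0% | 14.5% |
| 20% | 36.0% | 28.0% |

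For example, with w = 5% and c = 0.5: 1 - 0.95 × 0.975 = 7.4%.

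**4. Effect on a placebo contrast (illustrative)**

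Group sizes: protocol 11.4.3 puts 9% of subjects on placebo, and 0.09 × 66 = 5.9, about 6, leaving 60 active. If the ten active groups in SAP Table 2 are equal (an assumption, since Figure 1 is not shown), each has 6, and Cohorts A-C together have 36.

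Reaction rates: assume vaccine-period risks e of 50% and 10%, all falling in week 1, each combined with background b as p = 1 - (1 - e)(1 - b). With 5% weekly background and full capture in week 2:
- Seven days (b = 5%): 52.5% vs 14.5%, a difference of 38.0 points.
- Fourteen days (b = 9.75%): 54.9% vs 18.8%, a difference of 36.1 points.

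Power of the two-sided 5% Fisher test, 36 vs 6, by exact enumeration:

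| Weekly background | 7 days | 14 days, c = 1 | Loss |
|---|---|---|---|
| 5% | 29.0% | 26.5% | 2.5 points |
| 10% | 26.4% | 22.3% | 4.1 points |

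At c = 0.5 the 14-day power is 27.8% and 24.1%, so the losses are smaller still. The test is weak under either window.

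**The case against.** **The SAP statement can be defended.** It concerns the periods in which endpoint events are counted, and the protocol's endpoint definitions carry none. It names the diary as its source, and the diary card is not among the documents. A reader might infer that SAP section 8 is plainly false. The documents do not support that: the statement is defensible on the endpoint definitions and incomplete on the collection period. The diary may solicit to Day 14, in which case diary and protocol 8.7 disagree and need reconciling.

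**Week 2 is not uncollected.** A reader might also infer that Day 8-14 events are missed or are merely spontaneous reports. They are not: the diary remains in use, it is reviewed at the next visit, and AEs are recorded throughout. A diary handed in on Day 12 makes capture of Days 13-14 less structured but does not remove them. What stands is that the intensity of ascertainment changes within the window.

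**Background is not equally plausible for all terms.** SAP 7.1.1 counts injection-site preferred terms only, and a 5% to 10% weekly background is not credible for those. The argument applies mainly to myalgia, chills, rash, pyrexia and the ocular terms.

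**The consequence is limited.** Presentation is mainly descriptive, SAP 7.7 asks for caution with the tests, all events are listed, and a longer window keeps late reactions in view. This is a good reason to keep the 14-day figures, but not a reason to leave the two periods unseparated.

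**Conclusion.** The mismatch stands. Protocol 8.7 solicits for seven days, the SAP counts to Day 14 without a split, and SAP section 8 does not mention 8.7. Half of the post-vaccination days behind three co-primary endpoints are event-triggered.

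The effect is mainly on interpretation of the rates. At an assumed weekly background of 5% to 10%, the background part rises by about 2.4 to 9 percentage points (7.4 - 5 at half capture and 5% background; 19 - 10 at full capture and 10%). This applies to the systemic and ocular terms, and much less to the injection-site terms. The dilution of contrasts is modest: 2.5 to 4 points of power for an assumed 36 vs 6. These figures rest on assumed rates and group sizes; the textual finding does not.

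Two stronger conclusions are tempting and not supported. One is a large loss of power. Setting a placebo-like contrast of 50% vs 10% at 36 vs 12 gives bigger losses, but about 6 subjects are on placebo, and under equal groups 12 is the size of an active cohort. The other is that seven days must be the only co-primary window. That depends on a diary card that is not available here and is partly a matter of preference.

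**What to change.** 1. **SAP section 8.** State that protocol 8.7 sets a seven-day period for solicited events with event-triggered diary entries from Day 7 to Day 14. Say what the diary card asks for in each week, and reconcile the two.
2. **SAP 7.1.1 to 7.1.3.** Present Day 0-7 and Day 8-14 separately after each vaccination. Give the rates, 95% confidence intervals and Fisher tests on Day 0-7 alongside those for the 14-day window.
3. **Main window.** Use Day 0-7 as the main window unless the diary card is shown to solicit actively to Day 14. Settle this before unblinding.

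The cost is SAP wording, extra table columns and a repeated set of Fisher tests, which adds to the unadjusted tests that SAP 7.7 already asks readers to treat with care. Day 0-7 rates will be slightly lower than 14-day rates. No data collection changes, and later events remain in the 14-day columns, the TEAE tables and the listings.
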